13.4 Safety monitoring and stopping guidelines

Adverse events will be monitored during the trial. The occurrence of unacceptable AEs, as defined in **Section 5.6**, at any time during the treatment will be the endpoint for safety monitoring. If the events of unacceptable AEs appear to be higher than 33%, we will temporarily halt the study pending safety evaluation. A Beta (1.5, 5.5) prior, representing a toxicity rate of 21%, a slightly conservative estimate, was used in the development of the stopping guidelines. The therapy will be re-evaluated if the posterior probability that the toxicity rate exceeds the 33% boundary is greater than 60%. **Table 5** summarizes the stopping boundaries for unacceptable toxicities.

Table 5. The number of unacceptable toxicities needed to trigger stopping guidelines throughout the course of the study.

Number of Subjects	Number of unacceptable toxicities needed to trigger re-evaluation
2	2
3-5	3
6-7	4
5-10	5
11-13	6
14-16	7
17-19	8
20-22	9
23-25	10

Operating characteristics of the stopping rule based on 10000 simulations are shown below.

True probability of	Probability of triggering
unacceptable toxicity	stopping guidelines
5%	0.4%
10%	1.8%
15%	6%
20%	14%
25%	27.5%
30%	44.9%
35%	62.3%
40%	78%
45%	89.2%

REFERENCES

- 1. Rahib, L. *et al.* Projecting cancer incidence and deaths to 2030: the unexpected burden of thyroid, liver, and pancreas cancers in the United States. *Cancer Res.* **74**, 2913–2921 (2014).
- 2. Siegel, R. L., Miller, K. D. & Jemal, A. Cancer statistics, 2016. *CA Cancer J Clin* **66**, 7–30 (2016).
- 3. Burris, H. A. *et al.* Improvements in survival and clinical benefit with gemcitabine as first-line therapy for patients with advanced pancreas cancer: a randomized trial. *J. Clin. Oncol.* **15**, 2403–2413 (1997).
- 4. Conroy, T. *et al.* FOLFIRINOX versus Gemcitabine for Metastatic Pancreatic Cancer. *New England Journal of Medicine* **364**, 1817–1825 (2011).
- 5. Von Hoff, D. D. *et al.* Increased Survival in Pancreatic Cancer with nab-Paclitaxel plus Gemcitabine. *New England Journal of Medicine* **369**, 1691–1703 (2013).
- 6. Borazanci, E. *et al.* Adenosquamous carcinoma of the pancreas: Molecular characterization of 23 patients along with a literature review. *World J Gastrointest Oncol* 7, 132–140 (2015).
- 7. Brahmer, J. R. *et al.* Safety and activity of anti-PD-L1 antibody in patients with advanced cancer. *N. Engl. J. Med.* **366**, 2455–2465 (2012).

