5.6 Unacceptable Toxicity

Toxicities are defined in the Investigator's Brochure and **Table 4**. Unacceptable toxicities for this protocol that will trigger additional review described below are defined as:

- 1. Any treatment-related > grade 3 AEs. Exceptions include:
 - Asymptomatic laboratory abnormalities (AST, ALT, and bilirubin abnormalities requiring discontinuation as per **Table 4** will be considered unacceptable toxicity)
 - Grade 3 fatigue
 - Grade 3 dermatologic AEs that are considered mild in severity but only considered grade 3 because of >30% body surface involvement including pruritus
 - Diarrhea, nausea, or vomiting that resolves to < grade 3 within 48 hours of maximal intervention
 - Grade 3-4 hyperglycemia or grade 3 endocrinopathies where symptoms are controlled on hormone replacement therapy
- 2. Treatment related blood bilirubin > 5 x ULN or concurrent blood bilirubin > 2 x ULN and AST or ALT > 3 x ULN
- 3. Treatment related eye pain ≥ grade 2 or reduction of visual acuity that does not respond to topical therapy and does not improve to ≤ grade 1 severity within 2 weeks of starting therapy, or requires systemic therapy is an unacceptable toxicity.

Unexpected Grade 3 or greater laboratory abnormalities should be repeated within 24-72 hours if clinically indicated and monitored as necessary to determine if event meets toxicity criteria.

The proportion of treated subjects with unacceptable toxicity will be monitored using a Bayesian stopping guideline. A Beta (1.5, 5.5) prior, representing a toxicity rate of 21%, a slightly conservative estimate, was used in the development of our guidelines. We will halt the accrual and re-evaluate the safety if the posterior probability that the toxicity rate exceeds the 33% boundary is greater than 60%. Toxicity will be monitored continuously. **Table 2** summarizes the stopping boundaries for unacceptable toxicities.

Table 2. The number of unacceptable toxicities needed to trigger stopping guidelines throughout the course of the study.

Number of Subjects	Number of unacceptable toxicities needed to trigger re-evaluation
2	2
3-5	3
6-7	4
5-10	5
11-13	6
14-16	7
17-19	8
20-22	9
23-25	10

Table 3. Probability of triggering a re-evaluation based upon the proportion with an unacceptable toxicity for a range of true toxicity probabilities.

True probability of	Probability of triggering
unacceptable toxicity	stopping guidelines
5%	0.4%
10%	1.8%
15%	6%
20%	14%
25%	27.5%
30%	44.9%
35%	62.3%
40%	78%

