13. STATISTICAL CONSIDERATIONS

13.1 Study Design/Endpoints

Sample Size calculation and justification

Simon's two-stage optimal design will be used ¹⁸. The null hypothesis that the true disease control rate at 4 months is 5% will be tested against a one-sided alternative of 30% disease control rate at 4 months. In the first stage, 7 patients will be accrued. If there are zero patients with disease control by 4 months, the study will be stopped. Otherwise, 14 additional patients will be accrued for a total of 21 patients. The null hypothesis (disease control rate of 5%) will be rejected if 3 or more patients with disease control at 4 months are observed in stage 1 and 2 combined. This design yields a type I error rate of 0.064 (target type I error 0.1) and power of 90% when the true disease control rate is 30%. The probability of stopping the trial early for futility is 70% if the true DCR is 5%.

We plan to enroll 25 subjects to ensure 21 would be evaluable for DCR. As this is a rare tumor subtype patients will be recruited at several sites including Johns Hopkins Hospital, Memorial Sloan Kettering Cancer Center and the Mayo Clinic. We do not anticipate any difficulties in trial enrollment. We expect an accrual rate of at least 2 patients per month across the sites, completing trial enrollment in 12 months.

Patients are evaluable for DCR if they receive at least one dose of retifanlimab, and have at least one post-baseline tumor assessments or discontinue due to toxicity or clinical progression prior to post-baseline tumor assessments. The study plans to enroll 25 subjects to ensure 21 would be evaluable for the primary efficacy endpoint.

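### The trigger probabilities printed for the toxicity stopping guideline do not follow from the limits and the 33%/60% criterion printed with them; above a 33% toxicity rate they are 3.7 to 6.2 points too high

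*Combined protocol and SAP*

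**What the plan says.** Sections 5.6 and 13.4 describe the same guideline. Section 13.4 gives the prior: "A Beta (1.5, 5.5) prior, representing a toxicity rate of 21%, a slightly conservative estimate, was used in the development of the stopping guidelines". The trigger is that the "posterior probability that the toxicity rate exceeds the 33% boundary is greater than 60" per cent. Section 5.6 adds: "Toxicity will be monitored continuously".

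The limits are in Table 2 (Section 5.6) and again in Table 5 (Section 13.4). They run from 2 toxicities in 2 subjects to 10 in 23-25. In both copies one row is labelled 5-10, which overlaps the rows 3-5 and 6-7.

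The trigger probabilities are in Table 3 ("Table 3. Probability of triggering a re-evaluation based upon the proportion with an unacceptable toxicity for a range of true toxicity probabilities") and in an unnumbered table after Table 5, introduced by: "Operating characteristics of the stopping rule based on 10000 simulations are shown below". Both print 0.4, 1.8, 6, 14, 27.5, 44.9, 62.3, 78 and 89.2% for true rates of 5 to 45% in steps of 5.

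On the number treated, Section 13.1 says: "We plan to enroll 25 subjects to ensure 21 would be evaluable for DCR". Neither section states the sample size or the look schedule used in the simulation, or when a toxicity-free subject enters the count.

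**The concern.** Once the limits, the true rate and the looks are fixed, the trigger probability is determined and can be computed exactly. The printed column should therefore match that calculation to within simulation error, which for 10,000 runs is a standard error of at most 0.5 points. It does not.

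This column is the plan's only statement of how the guideline performs. Read against the printed limits, it claims more frequent triggering than they deliver when toxicity is above 33%, and more frequent halts than they would cause when toxicity is acceptable.

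**Working it through.** **Inputs.** Prior Beta(1.5, 5.5), limit 33% and cut-off 60% (Sections 5.6 and 13.4); continuous monitoring (Section 5.6), modelled as a look after each fully observed subject; N = 25, the last row of the limits and the planned enrolment (Section 13.1); 10,000 simulations (Section 13.4).

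**Step 1: reproduce the limits.** After x toxicities in n subjects the posterior is Beta(1.5 + x, 5.5 + n − x). The limit L(n) is the smallest x with P(rate > 0.33) > 0.60. Examples:

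- n = 2: x = 1 gives 0.330, x = 2 gives 0.621, so L = 2.
- n = 5: x = 2 gives 0.356, x = 3 gives 0.607, so L = 3.
- n = 8: x = 4 gives 0.597, x = 5 gives 0.787, so L = 5.
- n = 25: x = 9 gives 0.474, x = 10 gives 0.623, so L = 10.

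For n = 2 to 25 the result is 2; 3 (n = 3-5); 4 (6-7); 5 (8-10); 6 (11-13); 7 (14-16); 8 (17-19); 9 (20-22); 10 (23-25). That is every printed limit, with the row 5-10 read as 8-10.

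**Step 2: trigger probability.** Let f(n, x) be the probability of x toxicities after n subjects with no trigger so far, at true rate p. For x < L(n),

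f(n, x) = (1 − p)·f(n − 1, x) + p·f(n − 1, x − 1).

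Probability mass that reaches L(n) is removed as triggered. The trigger probability is 1 − Σ f(25, x). The standard error of a 10,000-run simulation is √[q(1 − q)/10,000], where q is the exact value.

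| True rate | Printed % | Exact %, N = 25 | Gap, points | Gap in SE |
|---|---|---|---|---|
| 5% | 0.4 | 0.34 | 0.1 | 1.1 |
| 10% | 1.8 | 1.75 | 0.05 | 0.4 |
| 15% | 6 | 5.10 | 0.9 | 4.1 |
| 20% | 14 | 11.72 | 2.3 | 7.1 |
| 25% | 27.5 | 22.83 | 4.7 | 11.1 |
| 30% | 44.9 | 38.33 | 6.6 | 13.5 |
| 35% | 62.3 | 56.05 | 6.2 | 12.6 |
| 40% | 78 | 72.67 | 5.3 | 12.0 |
| 45% | 89.2 | 85.46 | 3.7 | 10.6 |

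At a 40% rate the chance of no trigger by subject 25 is 100 − 72.7 = 27.3%, against 100 − 78 = 22% from the printed table.

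**Step 3: other readings.** Values at 35, 40 and 45%, against the printed 62.3, 78 and 89.2:

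- N = 21: 51.3, 67.1, 80.3.
- Looks at every second subject plus n = 25: 53.0, 70.4, 84.1.
- Row 5-10 taken literally (limit 5 at n = 5-7): 53.8, 71.1, 84.6.
- Limit 4 at n = 8, where the posterior of 0.597 just misses 0.60: 57.1, 73.4, 85.9.

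Extending the criterion past 25 subjects goes beyond the printed limits and the planned enrolment. The best fit for N between 15 and 60 is N = 34, which gives 0.3, 1.8, 5.1, 12.1, 24.5, 42.3, 62.4, 79.8 and 91.3%. It is still off by up to 3.0 points and 7.4 standard errors.

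**Step 4: could another rule have produced the column?** The same prior with a 30% limit and a 65% cut-off gives 0.4, 2.0, 6.1, 14.4, 27.9, 45.2, 63.2, 78.6 and 89.4%, within 1 point of the printed column throughout. That rule implies different limits, for example 4 instead of 5 at n = 8 and 9 instead of 10 at n = 23. This shows only that the column could describe a rule other than the printed one. It does not identify the cause.

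**The case against.** **The look model is assumed.** The plan does not say when a toxicity-free subject is counted. Suppose toxicities count at once and toxicity-free subjects enter the denominator two enrolments later. This scheme is assumed and is not in the documents; 200,000 simulated runs give 0.6, 2.8, 7.3, 15.2, 27.5, 43.3, 60.5, 76.0 and 87.4%. The gaps above 33% shrink to about 2 points. The values at 5 to 20% are then too high and those at 30 to 45% too low, by up to 6.3 standard errors, and a three-enrolment delay fits worse (up to 15.4). What stands is that the exact size of the gap depends on the counting scheme. The mismatch remains.

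**The 15% row is not secure.** It is printed as a whole number. If 6 was rounded from 5.5, the gap is 0.4 points, or 0.4/0.22 = 1.8 standard errors. That is fair. The 20% row survives the same allowance: 13.5 − 11.72 = 1.8 points, or 1.8/0.32, more than 5 standard errors.

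**Calling the column too high presumes that the limits are right.** The documents establish only that the two disagree. The limits do agree with the stated criterion, so they are the natural reference, but the intended rule is for the sponsor to confirm.

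**The consequence is small.** A trigger leads to a temporary halt and review, safety is discussed at weekly meetings (Section 12.2), and no efficacy quantity is affected. That is true, and it is why this is a correction to make and not a threat to the trial.

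**Conclusion.** The concern holds. For N = 25 with a look after each fully observed subject, the printed trigger probabilities exceed those of the printed rule by 6.2, 5.3 and 3.7 points at true rates of 35, 40 and 45%. The largest excess, 6.6 points, is at 30%, below the limit. The 5% and 10% rows agree, and the discrepancy is firm from 20% upward. N = 25 is the sample size from 21 to 25 that favours the printed column most; fewer subjects or fewer looks widen the gap.

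The table also overstates halts at an acceptable rate: 14% against 11.7% when the true rate is 20%. If the printed limits are the intended rule, no halt decision changes and only its stated properties are wrong. If the printed probabilities are the intended properties, the limits or the criterion do not deliver them. The documents do not allow the cause to be identified. The 5-10 row label is a separate slip that does not explain the mismatch.

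**What to change.** Reconcile the limits, the criterion and the probability column in Sections 5.6 and 13.4.

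- If the printed limits stand, replace both copies of the column with values computed from them. For N = 25 and a look after each fully observed subject these are 0.3, 1.75, 5.1, 11.7, 22.8, 38.3, 56.1, 72.7 and 85.5%.
- If the printed probabilities are the intended properties, disclose the rule that was simulated and bring the limits and the criterion into line with it.
- In either case, state the sample size, the look schedule and when a toxicity-free subject enters the count.
- Correct the row label 5-10 in Tables 2 and 5. The stated criterion gives 5 toxicities at 8-10 subjects.

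If the limits stand, the cost is nine figures and one label, each in two places, plus a sentence on the simulation settings. The stated protection becomes slightly less favourable.

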APPENDIX A: Performance Status Criteria

ECOG Performance Status Scale		Karnofsky Performance Scale			
Grade	Descriptions	Percent	Description		
0	Normal activity. Fully active, able to carry on all pre-disease	100	Normal, no complaints, no evidence of disease.		
U	performance without restriction.	90	Able to carry on normal activity; minor signs or symptoms of disease.		
Symptoms, but ambulatory. Restricted in physically strenuous activity, but ambulatory and able		80	Normal activity with effort; some signs or symptoms of disease.		
I	to carry out work of a light or sedentary nature (e.g., light housework, office work).	70	Cares for self, unable to carry on normal activity or to do active work.		
In bed <50% of the time. Ambulatory and capable of all self-care, but unable to carry out		60	Requires occasional assistance, but is able to care for most of his/her needs.		
	any work activities. Up and about more than 50% of waking hours.	50	Requires considerable assistance and frequent medical care.		
2	In bed >50% of the time. Capable of only limited self-care confined		Disabled, requires special care and assistance.		
to bed or chair more than 50% of waking hours.		30	Severely disabled, hospitalization indicated. Death not imminent.		
4 100% bedridden. Completely disabled. Cannot carry on any self-care. Totally confined to bed or chair.		20	Very sick, hospitalization indicated. Death not imminent.		
		10	Moribund, fatal processes progressing rapidly.		
5	Dead.	0	Dead.		

APPENDIX B: Response Evaluation Criteria in Solid Tumors (RECIST) 1.1 Criteria for Evaluating Response in Solid Tumors

RECIST version 1.1 will be used in this study for assessment of tumor response. While either CT or MRI may be used utilized, as per RECIST 1.1, CT is the preferred imaging technique in this study.

Disease Parameters

Measurable disease: Measurable lesions are defined as those that can be accurately measured in at least one dimension (longest diameter to be recorded) as \geq 20 mm by chest x-ray, as \geq 10 mm with CT scan, or \geq 10 mm with calipers by clinical exam. All tumor measurements must be recorded in millimeters (or decimal fractions of centimeters).

Note: Tumor lesions that are situated in a previously irradiated area might or might not be considered measurable unless there is evidence of progression in the irradiated site. Malignant lymph nodes. To be considered pathologically enlarged and measurable, a lymph node must be ≥15 mm in short axis when assessed by CT scan (CT scan slice thickness recommended to be no greater than 5 mm). At baseline and in follow-up, only the short axis will be measured and followed.

Non-measurable disease: All other lesions (or sites of disease), including small lesions (longest diameter <10 mm or pathological lymph nodes with ≥10 to <15 mm short axis), are considered non-measurable disease. Bone lesions, leptomeningeal disease, ascites, pleural/pericardial effusions, lymphangitis cutis/pulmonitis, inflammatory breast disease, and abdominal masses (not followed by CT or MRI), are considered as non-measurable.

Note: Cystic lesions that meet the criteria for radiographically defined simple cysts should not be considered as malignant lesions (neither measurable nor non-measurable) since they are, by definition, simple cysts.

'Cystic lesions' thought to represent cystic metastases can be considered as measurable lesions, if they meet the definition of measurability described above. However, if non-cystic lesions are present in the same subject, these are preferred for selection as target lesions.

Target lesions: All measurable lesions up to a maximum of 2 lesions per organ and 5 lesions in total, representative of all involved organs, should be identified as **target lesions** and recorded and measured at baseline. Target lesions should be selected on the basis of their size (lesions with the longest diameter), be representative of all involved organs, but in addition should be those that lend themselves to reproducible repeated measurements. It may be the case that, on occasion, the largest lesion does not lend itself to reproducible measurement in which circumstance the next largest lesion which can be measured reproducibly should be selected. A sum of the diameters (longest for non-nodal lesions, short axis for nodal lesions) for all target lesions will be calculated and reported as the baseline sum diameters. If lymph nodes are to be included in the sum, then only the short axis is added into the sum. The baseline sum diameters will be used as reference to further characterize any objective tumor regression in the measurable dimension of the disease.

Non-target lesions: All other lesions (or sites of disease) including any measurable lesions over and above the 5 target lesions should be identified as **non-target lesions** and should also be recorded at baseline. Measurements of these lesions are not required, but the presence, absence, or in rare cases unequivocal progression of each should be noted throughout follow-up.

Evaluation of Target Lesions

Complete Response (CR): Disappearance of all target lesions. Any pathological lymph nodes (whether target or non-target) must have reduction in short axis to <10 mm.

Partial Response (PR): At least a 30% decrease in the sum of the diameters of target lesions, taking as reference the baseline sum diameters.

Progressive Disease (PD): At least a 20% increase in the sum of the diameters of target lesions, taking as reference the smallest sum on study (this includes the baseline sum if that is the smallest on study). In addition to the relative increase of 20%, the sum must also demonstrate an absolute increase of at least 5 mm. (Note: the appearance of one or more new lesions is also considered progressions).

Stable Disease (SD): Neither sufficient shrinkage to qualify for PR nor sufficient increase to qualify for PD, taking as reference the smallest sum diameters while on study.

Evaluation of Non-Target Lesions

Complete Response (CR): Disappearance of all non-target lesions and normalization of tumor marker level. All lymph nodes must be non-pathological in size (<10 mm short axis).

Note: If tumor markers are initially above the upper normal limit, they must normalize for a subject to be considered in complete clinical response.

Non-CR/Non-PD: Persistence of one or more non-target lesion(s) and/or maintenance of tumor marker level above the normal limits.

Progressive Disease (PD): Appearance of one or more new lesions and/or *unequivocal progression* of existing non-target lesions. *Unequivocal progression* should not normally trump target lesion status. It must be representative of overall disease status change, not a single lesion increase.

Although a clear progression of "non-target" lesions only is exceptional, the opinion of the treating physician should prevail in such circumstances, and the progression status should be confirmed at a later time by the review panel (or Principal Investigator).

Evaluation of Best Overall Response

The best overall response is the best response recorded from the start of the treatment until disease progression/recurrence (taking as reference for progressive disease the smallest measurements recorded since the treatment started). The subject's best response assignment will depend on the achievement of both measurement and confirmation criteria.

For Subjects with Measurable Disease (i.e., Target Disease)

Target Lesions	Non-Target Lesions	New Lesions	Overall Response	Best Overall Response when Confirmation is Required*
CR	CR	No	CR	≥4 wks. Confirmation**
CR	Non-CR/Non-PD	No	PR	
CR	Not evaluated	No	PR	\geq 4 wks.
PR	Non-CR/Non-PD/not evaluated	No	PR	Confirmation**
SD	Non-CR/Non-PD/not evaluated	No	SD	Documented at least once \geq 4 wks. from baseline**
PD	Any	Yes or No	PD	
Any	PD***	Yes or No	PD	no prior SD, PR or CR
Any	Any	Yes	PD	

^{*} See RECIST 1.1 manuscript for further details on what is evidence of a new lesion.

Note: Subjects with a global deterioration of health status requiring discontinuation of treatment without objective evidence of disease progression at that time should be reported as "symptomatic deterioration." Every effort should be made to document the objective progression even after discontinuation of treatment.

Reference

E.A. Eisenhauer, P. Therasse, J. Bogaerts, L.H. Schwartz, D. Sargent, R. Ford, J. Dancey, S. Arbuck, S. Gwyther, M. Mooney, L. Rubinstein, L. Shankar, L. Dodd, R. Kaplan, D. Lacombe, J. Verweij. New response evaluation criteria in solid tumours: Revised RECIST guideline (version 1.1). Eur J Cancer. 2009 Jan;45(2):228-47.

^{**} Only for non-randomized trials with response as primary endpoint.

^{***} In exceptional circumstances, unequivocal progression in non-target lesions may be accepted as disease progression.

